2.3 Hypotheses

Based on the first specific objective, two hypotheses to be tested are:

H1a: There is significant difference of medication adherence level among participants before and after the intervention.

H1b: There is significant difference of medication adherence level after the intervention between participants from intervention group and control group.

Based on the second specific objective, six hypotheses to be tested are:

H2a: There is a significant relationship between attitude to adherence and intention to adhere.

H2b: There is a significant relationship between subjective norm to adherence and intention to adhere.

H2c: There is a significant relationship between perceived behavior control to adherence and intention to adhere.

H2d: There is a significant relationship between perceived behavior control to adherence and medication adherence.

H2e: There is a significant relationship between intention to adherence and medication adherence.

H2f: There is a moderating effect by adherence information between intention to adhere and medication adherence.

Based on the third specific objective, five hypotheses to be tested are:

H3a: There is significant difference of attitude to adhere after the intervention between participants from intervention group and control group.

H3b: There is significant difference of subjective norm to adhere after the intervention between participants from intervention group and control group.

H3c: There is significant difference of perceived behavioural control to adhere after the intervention between participants from intervention group and control group.

H3d: There is significant difference of intention to adhere after the intervention between participants from intervention group and control group.

H3e: There is significant difference of adherence information after the intervention between participants from intervention group and control group.

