3.9 Outcome measurement

Primary outcome:

A validated 8-item Malay version of Medication Adherence Scale (MALMAS) will be employed to assess the level of medication adherence among Sarawak patients (Chung et al. 2015). All the items were translated into Bahasa Malaysia and were back translated to English by a group of four experienced language lecturers from University of Malaysia Sarawak.

Secondary outcome:

The psychosocial variables of Theory of Planned Behaviour and adherence information variable from IMB will be employed as secondary outcome of this study. The sources of the items to measure all the variables in conceptual framework are depicted in Table 4.

Paper-based questionnaires will be distributed to the targeted patients by trained enumerators during the group based intervention. Prior to answering the survey, subjects will be briefed about the structure of the questionnaire and how to answer the questions by main facilitator. Any enquiries raised by the respondents will be explained by facilitators.

Table 4: Instrument for the study

Variable	No. of items	Measuring scale	Adopted from
Adherence information	6	5 points Likert scale	McPherson et al. 2008
Attitude to adhere	5	5 points Likert scale	Farmer et al. 2006

Subjective Norm to adhere	6	5 points Likert scale	Farmer et al. 2006
Perceived Behavioural Control to adhere	11	5 points Likert scale	Fernandez et al. 2008
Intention to adhere	3	5 points Likert scale	Vissman et al 2013
Medication adherence	8	1-7 items are measured with binomial answers which are “yes” or “no”; the last item is measured with 5 points Likert scale	Chung et al. 2015
Demographic	15	(1) enrolled with diabetic MTAC; (2) numbers of medications, one or more than one; (3) frequency of the medications, a once-daily dose or more frequent; (4) age; (5) gender; (6) highest education level; (7) monthly household income; (8) employment status; (9) having complications; (10) taking traditional complementary and alternative medicines; (11) residential area, urban or rural; (12) living condition, having social support or stay individually; (13) undergone diabetic education by diabetic nurse; (14) newly diagnosed or established T2DM; (15) concurrent diseases	

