3.11.2 Data analysis for first objective

The first objective of this study is to measure the effectiveness of the intervention in improving medication adherence. Descriptive statistics will be used to present the results on the level of medication adherence before and after the intervention. Mann-Whitney U test will be used to examine the change of patients between adherent patients (MALMAS > 6) and non-adherent patients (MALMAS < 6) before and after the intervention within same group. In terms of inter-group comparison for the medication adherence level (adherent vs non-adherent) before and after the intervention, Wilcoxon signed-rank will be executed.

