3.11.4 Data analysis for third objective

The third objective is to measure the impact of the intervention on psychosocial variables among participants. The change of the psychosocial variables before and after the intervention within the groups will be tested using paired t test. While the change of psychosocial variables before and after the intervention between the groups will be tested using independent t test.

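### The two tests for the primary outcome are transposed: an independent-samples test for before/after change and a paired test for intervention versus control, so H1b has no usable test

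*Protocol*

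**What the plan says.** Protocol section 2.3 sets two hypotheses for the first objective. The first, H1a, concerns change over time: "There is significant difference of medication adherence level among participants before and after the intervention". The second, labelled H1b, sets the two arms against each other: "There is significant difference of medication adherence level after the intervention between participants from intervention group and control group".

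The outcome is the MALMAS score (section 3.9): "A validated 8-item Malay version of Medication Adherence Scale (MALMAS) will be employed to assess the level of medication adherence".

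Section 3.11.2 then names the tests. For change over time: "Mann-Whitney U test will be used to examine the change of patients between adherent patients (MALMAS > 6) and non-adherent patients", with the scope given as "before and after the intervention within same group". For the arms: "In terms of inter-group comparison for the medication adherence level (adherent vs non-adherent) before and after the intervention, Wilcoxon signed-rank will be executed".

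Section 3.11.4 handles the same two kinds of comparison for the psychosocial variables. Within groups: "The change of the psychosocial variables before and after the intervention within the groups will be tested using paired t test". Between groups it names the independent t test.

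**The concern.** The Mann-Whitney U test compares two independent samples. The Wilcoxon signed-rank test works on differences within matched pairs. Section 3.11.2 uses the first where the data are paired and the second where they are independent.

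This is the only analysis that the protocol states for its primary outcome, and no other section gives a between-arm test for it. H1b carries the trial's claim of effectiveness. Followed literally, H1b is left with a test that has no pairs to work on, and H1a is tested with the pairing thrown away. If an analyst corrects this silently after the data are in, the primary test has changed without a record.

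**Working it through.** **1. What the design implies**

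| Comparison | Data structure | Source | Test in 3.11.2 | Test in 3.11.4 |
|---|---|---|---|---|
| Before v after, same group (H1a) | Paired | 2.3 | Mann-Whitney U (independent) | Paired t |
| Intervention v control (H1b) | Independent | 2.3, 3.1, 3.6, 3.7 | Wilcoxon signed-rank (paired) | Independent t |

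Section 3.1 describes a parallel two-group trial, section 3.6 simple randomisation without matching, and section 3.7 independent subjects in a 1:1 ratio. Section 2.4 calls the trial cluster randomised, but that would not create pairs of participants either.

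**2. The plan's own sample size**

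Inputs from section 3.7: difference 1, SD 1.8, power 0.90. Alpha is not stated for this calculation, so two-sided 0.05 is assumed.

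n per group = 2(z₀.₉₇₅ + z₀.₉₀)²σ²/δ² = 2 × (1.960 + 1.282)² × 1.8² / 1² = 2 × 10.51 × 3.24 = 68.1, rounded up to 69.

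The stated 69 reproduces as an unpaired two-sample calculation, so the trial was sized for an unpaired comparison.

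**3. Signed-rank between arms (H1b)**

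- *Unequal arms.* The test needs one partner per participant; with 60 v 69 it returns an error. If each of 138 completers is equally likely to be in either arm, P(exactly 69 and 69) = C(138, 69)/2¹³⁸ = 0.068, so P(unequal) = 1 − 0.068 = 0.93.
- *Equal arms, paired by row, score.* One simulated data set (69 per arm, SD 1.8) had Mann-Whitney p = 0.038. Over 3,000 arbitrary pairings of the same data, signed-rank p ran from 0.003 to 0.152 and was below 0.05 in 68% of them.
- *Equal arms, paired by row, adherent or not.* Assume 154 completers per arm (0.7 × 221 = 154.7) and 45 v 62 adherent (29% v 40%). The uncorrected chi-square gives a difference of 17/154 = 0.110, a standard error of √(0.347 × 0.653 × 2/154) = 0.0543, z = 2.03 and p = 0.042. Signed-rank over 2,000 arbitrary row orders gave p from about 0.02 to 0.07, non-significant in about 17%.
- *Before/after values pooled over both arms.* This reading does not test H1b. With no difference between arms, an assumed common shift of 0.3 or 0.5 points and an assumed correlation of 0.5, signed-rank rejects in 49% or 89% of runs.

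**4. Mann-Whitney on before/after scores (H1a)**

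The test's variance assumes independence. With rank correlation ρₛ between before and after, the true variance is about (1 − ρₛ) times the assumed one. The true size at nominal 5% is therefore about 2[1 − Φ(1.96/√(1 − ρₛ))]. For normal scores with correlation r, ρₛ = (6/π)·arcsin(r/2).

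| Assumed r | ρₛ | 1.96/√(1 − ρₛ) | True size |
|---|---|---|---|
| 0.3 | 0.288 | 2.32 | 2.0% |
| 0.5 | 0.483 | 2.73 | 0.6% |
| 0.7 | 0.683 | 3.48 | 0.05% |

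Simulation agrees: 2.3% at r = 0.3, 0.3% to 0.75% at r = 0.5, and at most 0.1% at r = 0.7. For an assumed shift of 0.5 points with 69 participants, simulated power is about 0.3 for Mann-Whitney at all three correlations, against 0.45, 0.62 and 0.83 for signed-rank.

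**5. With the tests exchanged**

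Mann-Whitney between arms (69 per arm, difference 1, SD 1.8) has simulated type I error of about 0.05 and power of about 0.89, in line with the planned 0.90. Signed-rank within an arm has simulated type I error of 0.045 to 0.055.

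**The case against.** The strongest reply is that this is a slip of the pen. Section 3.11.4 shows that the authors know the distinction, nothing in recruitment or data collection depends on it, and it can be put right before analysis.

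Four narrower objections have force.

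- Signed-rank between arms is not biased in every case. If the arms happen to be equal and rows are paired without regard to outcome, it keeps its nominal size (simulated 0.048 to 0.052) and has nearly the same power as Mann-Whitney (0.88 for both at the protocol's figures). This stands. What remains is that the result depends on an arbitrary row order and that the test fails when arms are unequal.
- The 29% v 40% example uses rates that the protocol does not give, and it sits at the threshold: the continuity-corrected chi-square gives p = 0.056 and Fisher's exact test 0.055. It illustrates dependence on row order and predicts nothing about this trial.
- The size and power figures for H1a are for scores, while section 3.11.2 speaks of adherent and non-adherent status. Entry requires a MALMAS score below 6 (section 3.4.1), so if screening is the baseline, everyone starts non-adherent and no before/after correlation exists for the status. This stands too.
- The H1a error is conservative: it loses power and does not create false positives.

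None of these makes the stated assignment right.

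**Conclusion.** The concern holds. Section 3.11.2 assigns a paired test to independent arms and an independent-samples test to paired data. This conflicts with the trial's design, with its own sample-size calculation and with section 3.11.4. It is a wrong rule stated in the protocol, not detail left for later, and it must be fixed because H1b has no other test.

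The conclusion rests on the documents alone. The sizes rest on assumptions: two-sided alpha of 0.05, normally distributed scores, before/after correlations of 0.3 to 0.7, within-group shifts of 0.3 to 0.5 points, and the 29% and 40% adherence rates. The 93% chance of unequal arms assumes 138 completers who are each equally likely to be in either arm.

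**What to change.** Rewrite the two sentences in section 3.11.2.

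- **Between arms (H1b):** an independent-samples method. Mann-Whitney U on the MALMAS score matches the section 3.7 calculation. If adherence status is to be compared, use a chi-square test or logistic regression.
- **Within arm (H1a):** a paired method, namely Wilcoxon signed-rank on the score or McNemar on the status. If screening is the baseline, McNemar can fill only one discordant cell, and regression to the mean alone could produce a significant change. Evidence of effectiveness should therefore come from H1b.

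State which of score or status is primary, and place a score of exactly 6, which currently falls in neither category.

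The cost is two sentences, with no new data or staff. The 69 per group is unchanged if the score is analysed. If the binary status becomes primary, section 3.7 needs a calculation for proportions, since the present one is for means. The change should be made and dated before the outcome data are analysed.

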3.11.3 Data analysis for second objective

The second objective is to test the predictive capacity of the integrated model. For that, path analysis using Partial Least Square-Structural Equation Model (PLS-SEM) with SmartPLS 3.0 software will be conducted.

3.11.4 Data analysis for third objective

The third objective is to measure the impact of the intervention on psychosocial variables among participants. The change of the psychosocial variables before and after the intervention within the groups will be tested using paired t test. While the change of psychosocial variables before and after the intervention between the groups will be tested using independent t test.

3.13 Treatment Fidelity

Treatment fidelity of the SGBI will be evaluated using the concept and strategies developed by the Treatment Fidelity Workgroup of the National Institutes of Health Behavior Change Consortium (Bellg et al 2004). The framework of treatment fidelity strategies for this study is depicted in Table 5.

Table 5: Framework of treatment fidelity strategies

Components	Goal	Strategies
Study design	
Ensure same treatment dose within conditions and equivalent dose across conditions.
	
(1) SGBI is designed to be completed within 3 hours with allowance of 15 minutes' deviation.
 
(2) The use intervention manual will ensure all facilitators conduct the intervention in a consistent manner.
 
(3) Observation on three sessions of intervention conducted by involved facilitators prior to actual study will be done by researchers to assess the consistency and appropriateness in conducting the intervention. Feedback will be given to the facilitators by observers after the observation. The facilitators will also discuss the issues faced during the intervention with researchers.
 
(4) All facilitators are acquired to adhere with the time allocated for each activity throughout the intervention.

	
Plan for implementation setbacks.
	
Have extra four qualified and trained facilitators in case of unavailability of the involved facilitators.

Provider training	Standardize training.	All the qualified and involved facilitators together with four backup facilitators will be trained together to ensure the consistency in conducting the intervention. Observation on three sessions of intervention conducted by involved facilitators prior to actual study will be able to ensure the actual performance of the involved facilitators.
	Ensure provider skill acquisition.	A scoring scale to assess the qualification and consistency of facilitators in conducting the intervention will be practiced.
	Minimize “drift” in provider skills.	During the actual study, researchers will still observe the intervention conducted by facilitators and will be video recorded to ensure the consistency of intervention. Should researcher observe less than 90% of consistency as compared to training sessions, the reasons that cause the inconsistency will be investigated and reported.
	Accommodate provider differences.	All the facilitators are pharmacists who work in Pharmaceutical Services Division, Sarawak State Health Department. Hence, the facilitators are having similar pattern of knowledge background and are considered expert related to the study.
Treatment delivery	Control for provider differences.	Facilitators having similar background and having same training at the same time

	Reduce differences within treatment.	Scripted intervention protocol is available and used by facilitators
	Ensure adherence to treatment protocol.	During the actual study, researchers will still observe the intervention conducted by facilitators and will be video recorded to ensure the consistency of intervention. Should researcher observe less than 90% of consistency as compared to training sessions, the reasons that cause the inconsistency will be investigated and reported.
	Minimize contamination between conditions	This is a randomization controlled trial with double blinding
Treatment receipt	Ensure participant comprehension.	
(1) The participant understanding on the message will be evaluated with the scales developed to measure the impact of the intervention on psychosocial variables of participants. Comparison between the intervention group and control group will show whether the improvement in the psychosocial variables is due to chance or is because of the intervention.
 
(2) Qualitative interview after the intervention will enable the researchers to know how the intervention impact their medication taking behaviour.

	Ensure participant ability to use cognitive skills.	
(1) Conduct structured interviews with participants;
 
(2) Facilitators work with participants until they can demonstrate correct medication taking skills.
 
(3) Hypothetical situations that participants may face in real life will be addressed during group discussion and sharing on their reasons of nonadherence and the method that they will adopt to overcome the problem.

	Ensure participant ability to perform behavioural skills.	Facilitators work with participants until they can demonstrate correct medication taking skills.
Enactment of treatment skills	Ensure participant use of cognitive skills.	The use of medication chart prepared by the participants will show how well they comprehend the medication taking skills.
	Ensure participant use of behavioural skills	Medication adherence will be measured after one, three and six months of intervention to ensure the messages conveyed through the intervention are translated into action and such action is maintained.

3.14 Ethical Consideration

All the data are restricted to the principal investigators and solely used for research purposes. Study will be conducted in compliance with ethical principles outlined in the Declaration of Helsinki and Malaysian Good Clinical Practice Guideline. This trial will be registered with Medical Research and Ethics Committee (MREC), National Institutes of Health Malaysia prior to the actual study. Besides, it will be registered with ClinicalTrials.gov following the approval from MREC.

3.15 Informed Consent/Assent Process and Subject Withdrawal

The informed consent forms will be first given and the purpose of the study will be explained to the respondent, in order to obtain the permission to participate in the study. They will be informed that their participation is voluntary and they have full rights to stop or refused to continue the study at any point of the survey. No penalty or benefits would be given once they stopped or completed the study. All the information given is strictly for research purposes and accessible by principle and co-investigators only. Participants will be informed through phone call if there were new information relevant to the consent.

In situation where the researcher found that a participant is no longer eligible or suitable for this study and decide to terminate the participant, or a participant decides to withdraw from this study, the following steps of subject withdrawal will be executed (Education & Magazines 2009).

Firstly, the principal investigator will ask the participant who is withdrawing or terminated, whether the participant intend to provide subsequent follow-up and further data collection after withdrawal or termination from the interventional portion of the study. If the participant agrees to continue with subsequent follow-up and data collection, a new informed consent form for limited participation in this study should be obtained. If the participant doesn't agree to continue with

subsequent follow-up and data collection, no medical records or other confidential records which requiring informed consent will be accessed by any investigator of this study. Meanwhile, only the data collected prior to the participant's withdrawal or termination can be accessed, reviewed and remained as part of the study database. Notably, such data should not be removed and should be included for data analysis to avoid a situation called "informative censoring", which could undermine the validity of this study. Data analysis technique namely intention-to-treat analysis or data imputation will be performed to overcome the withdrawal or termination of the participants. Lastly, the timing and reason of withdrawal or termination of any participant will be reported by the principal investigator.

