3.7 Sample size

We are planning a study of a continuous response variable from independent control and experimental subjects with 1 control per experimental subject. In a previous study (Butt et al. 2016), the response within each subject group was normally distributed with standard deviation 1.8. If the true difference in the experimental and control means is 1, we will need to study 69 experimental subjects and 69 control subjects to be able to reject the null hypothesis that the population means of the experimental and control groups are equal with probability (power) 0.9 (Dupont and Plummer 1998). By estimating 30% of dropout or incomplete data, a minimum sample size 180 with 90 for both groups are pre-determined for each study sites.

On the other hand, to test the integrated model as mentioned in second objective, with effect size f square equal to 0.15, α error probability equals to 0.05, power equals to 0.95 and total number of predictors equal to 3, total sample size required will be 170 (Faul et al 2009). Assuming 30% of dropout or incomplete data, a minimum sample size 221. As a result, a total minimum sample size of 442 with 221 for both groups are acquired.

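### Section 3.15 treats intention-to-treat and imputation as alternatives; taken alone, intention-to-treat leaves the named tests as complete-case analyses at each visit, against 3.15's own rule on withdrawn participants' data

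*Protocol*

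**What the plan says.** Section 3.15 is the only place where the protocol says how withdrawals enter the analysis. Data collected before a participant leaves are to be kept: "such data should not be removed and should be included for data analysis to avoid a situation called 'informative censoring". The remedy follows: "Data analysis technique namely intention-to-treat analysis or data imputation will be performed to overcome the withdrawal or termination of the participants". No rule says which of the two applies, or when. The same section lets a participant leave the interventional part but consent to further follow-up.

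Section 3.7 sizes the trial with an allowance for loss: "By estimating 30% of dropout or incomplete data". It closes with "a total minimum sample size of 442 with 221 for both groups are acquired".

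Section 3.11.2 compares arms on adherence status: "In terms of inter-group comparison for the medication adherence level (adherent vs non-adherent) before and after the intervention, Wilcoxon signed-rank will be executed". Section 3.11.4 uses a paired t test for psychosocial change within groups and an independent t test for that change between groups. Neither section mentions an analysis set, imputation or a method that uses incomplete records. Adherence is measured at 1, 3 and 6 months (3.13, Table 5). Every participant has a T0 score, because a MALMAS score below 6 is an entry criterion (3.4.1, 3.5).

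**The concern.** Intention-to-treat is a rule about the population and the arm. It does not produce an outcome for someone who was not measured. Imputation produces outcomes and is silent on population and arm. A trial with missing outcomes needs both a rule on who is analysed and a method for missing values. Joining the two by 'or' allows the first to be chosen without the second.

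Under that choice, a paired or change-score test needs an observed value at the visit compared. A participant with a T0 score and no later value then adds nothing, although 3.15 wants such data included precisely to guard against informative loss. The stated safeguard would not be delivered by the stated analysis.

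Loss that depends on arm and on adherence is possible on the protocol's own account. The intervention session lasts 180 minutes (Table 3), while controls only complete a questionnaire (3.8.2). Section 3.6 accepts that controls will be able to tell their assignment. The outcome is self-reported (2.4).

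**Working it through.** **Inputs from 3.7.** Planned difference 1; SD 1.8 ("the response within each subject group was normally distributed with standard deviation 1.8"); power 0.90; 69 per group before loss; 30% allowance; total 442. Two-sided alpha of 0.05 is an assumption for the first objective, since 3.7 states 0.05 only for the second.

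**1. Reproduce the plan's figures.**
- n per group = 2 × (1.960 + 1.282)² × 1.8² / 1² = 68.1, rounded up to 69. This agrees with 3.7.
- Allowance for loss: 69 × 1.3 = 89.7, so 90; and 170 × 1.3 = 221. Both agree with 3.7.

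**2. Power if only observed values are used and 30% are missing.**
- Whole trial: 442 × 0.70 = 309.4, so 154 to 155 per arm. Power for a difference of 1 is about 0.998.
- One site alone: 180 × 0.70 = 126, so 63 per group. Power is 0.877 (normal approximation) or 0.872 (exact t).
- At the stated total, power is not the issue.

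**3. Bias on the score (illustration).** Let C be the mean of completers in an arm, L the mean that those lost would have had, and f the fraction lost.
- Full-arm mean = (1 − f)C + fL, so complete-case error = C − full-arm mean = f(C − L).
- Assume f = 0.30, C − L = 0.5 to 1.0 in one arm, and no gap in the other.
- Error = 0.30 × 0.5 = 0.15 to 0.30 × 1.0 = 0.30 points, or 15% to 30% of the planned difference of 1.
- If the affected arm is the intervention arm, the benefit is overstated; if it is control, the benefit is understated.

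**4. Bias on the dichotomy that 3.11.2 compares (illustration).** Assume true adherence of 30% in both arms and about 30% missing in each, at random in one arm.
- Other arm loses 20% of adherent and 34.3% of non-adherent: observed adherence = 0.30 × 0.80 / (0.30 × 0.80 + 0.70 × 0.657) = 0.240 / 0.700 = 34.3%. False difference: 4.3 percentage points.
- Other arm loses 10% and 38.6%: 0.30 × 0.90 / (0.30 × 0.90 + 0.70 × 0.614) = 0.270 / 0.700 = 38.6%. False difference: 8.6 points.

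**5. Where the omission applies.** It arises only if nothing is imputed, and visit by visit: a participant missing only month 6 still counts at months 1 and 3. The Mann-Whitney test, which 3.11.2 assigns to the before-after comparison within a group, could keep an unpaired T0 value, but that does not help the comparison between arms.

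**The case against.** The best defence is that 3.15 describes two kinds of participant. Some leave the intervention but agree to follow-up; their outcomes exist, and intention-to-treat is the right principle for them. Others refuse follow-up, and imputation suits them. On that reading 'or' means whichever fits. It is a fair reading, but the text does not say it. The sentence offers both techniques for withdrawal or termination in general, and nothing prevents the first from being used alone.

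A second defence is that analysis sets, imputation models and sensitivity analyses may sit in a statistical analysis plan that is not shown. That stands: their absence is not the point. The point is a rule that 3.15 does state and that, on one of its two branches, fails the aim set beside it.

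Three stronger readings are tempting and not supported:
- That the named tests discard every participant with a missing follow-up. The loss is conditional on not imputing and applies per visit.
- That participants might be regrouped by treatment received. No section proposes this, and hypothesis H1b in 2.3 compares intervention with control.
- That 30% differential withdrawal is expected. The figure in 3.7 is a sample-size allowance that also covers incomplete data. Nor is the trial wholly open: participants and facilitators learn the allocation at the session, but 3.6 keeps researchers blinded.

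**Conclusion.** The point holds in a limited form. Section 3.15 presents as interchangeable two techniques that do different jobs. If intention-to-treat is used without imputation, the paired and change-score tests in 3.11.2 and 3.11.4 become complete-case analyses at each visit, which contradicts 3.15's instruction to include withdrawn participants' data.

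The harm is possible bias that the sample size does not cure. Its size cannot be derived from the documents. The shift of 0.15 to 0.30 points rests on an assumed gap of 0.5 to 1.0 points confined to one arm, and it is on the score scale, whereas 3.11.2 compares adherent with non-adherent. The 4.3 and 8.6 percentage points on that dichotomy rest on assumed loss rates too. A reader should not take either as a forecast.

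**What to change.** - **3.15:** replace 'or' by 'and', and state that all randomised participants are analysed in their assigned arm. This statement would govern 3.11.4 as well.
- **3.11.2:** compare arms with a mixed model for the MALMAS score, with T0 and months 1, 3 and 6 as repeated measurements, arm means set equal at T0, arm by visit, and site. With T0 as an outcome, participants who have only T0 data stay in the model under missing at random; with T0 as a covariate they would drop out. The score is also the scale on which 3.7 sizes the trial. The adherent/non-adherent comparison can remain as a supporting analysis.
- **Sensitivity:** add a delta-adjusted imputation over a stated range of shifts, allowed to differ by arm. The mixed model alone does not remove bias if loss depends on unobserved scores.

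**Cost:** wording in 3.15 and 3.11.2, some extra analysis work, and a real change of the main test from the dichotomy to the score, which should be settled before any outcome data are examined. No further participants or visits are needed.
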